## **6.0 Reporting**

This study will have a Data Monitoring Committee. The details of this Committee and procedures for reporting are described in our Data Analysis Plan (Appendix 7). The appropriate local ISO(s) and PO(s) will be notified within one hour of the PI determining improper use or disclosure.

## **7.0 Privacy and Confidentiality**

This study will collect and use, but not disclose, subjects' Protected Health Information (PHI). Data will not be banked. Biological specimens are not utilized in this study.

Prior to the start of research, study investigators will have completed required VA R&D committee training (i.e., VA's Cyber Security Awareness course and Overview of Good Clinical Practice and Human Subjects Protection course) as well as other required trainings by IRB. Research staff and all site investigators will complete all required VA R&D and IRB research trainings, such as Collaborative Institutional Training Initiative courses on responsible practice of research and protection against risk. If a study member is no longer a part of the research team,

their access to research study data will be removed.

To protect against the potential loss of confidentiality, all electronic data will be coded, or de-identified to the extent possible, and stored on a secure, password-protected VA server. A “key” file will connect participant names and contact information with their study ID number; this file will be kept on a secured server behind the VA firewall and only be accessible to study personnel. Any paper data collected will be kept in a locked cabinet in secure (locked) office space at each VA site, until it can be scanned to an electronic file and the hard copy destroyed. Computerized files will be protected by the electronic firewall at the Roudebush VAMC and will be password protected (Roudebush servers behind VA firewall will be accessible to and used by study personnel at all sites, including Hines and St. Louis). Passwords are created according to guidelines set by the VA Office of Cyber and Information Security. All research records will be retained in accordance with the VHA Records Control Schedule. Study records will be destroyed in accordance with VHA Records Control Schedule as written at the time of study closure and in accordance with any revision to VA RCS after that time.

To protect against discomfort that may be experienced related to personal disclosure during CBTw and psychoeducation group sessions, participants will be explicitly informed that personal sharing is not mandatory and they have the right not to disclose information and/or speak during groups at their discretion. This is a standard practice in psychotherapy and education-based groups in clinical and research contexts. Second, “group rules” will be laid out at the beginning of the CBTw and psychoeducation conditions during the first group session in which confidentiality and respect for the privacy of other veterans will be discussed and agreed upon by all participants. Specifically, information discussed in the group will stay in the group and is not to be discussed with other persons outside of the group. Forming these “group rules” is also standard practice in research and clinical group therapy and psychoeducation settings.

During assessments, all participants will be instructed that they may refuse to answer any question that they are uncomfortable answering. In addition, participants may withdraw from the study at any time without any repercussions; participants will continue to receive all VA care and rehabilitation services (including supported employment) as usual, regardless of their study status.

During key informant staff interviews (Aim 3), all staff participants will be instructed that they may refuse to answer any question they are uncomfortable answering and they may end the interview at any time.

## **8.0 Communication Plan**

This project has multiple means of ensuring all study sites remain informed of current study events and changes. The study will utilize one project manager to oversee research assistants, other study personnel, and daily study procedures at all sites. Study team meetings will occur on a monthly basis to keep study sites informed of changes to the protocol, informed consent, the occurrence of Serious Adverse Events, Unanticipated Problems, and interim results. The project manager will lead weekly site calls via telephone will occur to discuss progress, plan, and troubleshoot with local site investigators and research staff at each site. Weekly consultation calls lead by [name] (PI) will take place with CBTw intervention facilitators at each site. Moreover, the PI will make periodic visits to each site for training and data collection. These forms of contact will be used to ensure the study is conducted according to the IRB-approved protocol.

Statistical Analysis Plan

Protocol Number: CIRB 20-08

Work as a determinant of health: A pragmatic trial of enhanced cognitive behavioral therapy to competitive work and wellness in veterans with serious mental illness (WORKWELL)

Funding Agency: HSR&D

9/30/2025

Analysis Plan

Statistical Considerations

Sample size and power

276 total participants will be needed to ensure > 80% power for this two-arm trial, accounting for the clustering effect of CBTw group cohort and potential attrition of 13%.

Aim 1: Work outcomes. The primary analysis is intention-to-treat and the primary outcome is total weeks worked in competitive jobs with primary endpoints of 6 and 9 months. Power estimate for total weeks worked was calculated using simulated data from a three-level linear regression model to account for the nested structure of the data. Simulation studies are the most flexible method for power analysis which can be tailored to any kinds of analyses. SAS 9.4 was used to generate 1000 datasets from each hypothesized model with plausible effect sizes for parameters of interest based on pilot data. Power estimates are based on the percentage of the datasets (replications) in which the parameters were significant. Based on the open trial pilot data, an ICC of .077 was estimated for the clustering effect of cohort and an ICC of .2 for repeated measures. Our pilot data show that CBTw significantly increased total weeks worked at 6 months ($f^2 = .15$). It is anticipated that there will be a larger increase in total weeks worked over time for the treatment arm. With the target sample size, there will be 97.6% power to detect even a small study arm by time interaction effect ($f^2 = .03$) with type I error set at .05. Further, the outcome distribution is likely to be non-normal. Although power will be attenuated by this non-normality, power to detect the target effects is still expected to be sufficient (>80%). For the binary outcome of achievement of steady competitive work, CBTw pilot data show that 49% of participants who were unemployed at baseline became steady workers at 6 months. In WORKWELL, it is expected that 5-10% more participants will acquire work and become steady workers during by the 9 month follow-up. Thus, power estimates may be conservative. In the control arm, it is anticipated that approximately 34% will become competitively employed and a lesser number will be steady workers by 9 months, based on VHA program evaluation data reporting 1-year SE outcomes. Based on the effect size, simulated data was used from two level logistic regression models, finding that the target sample size will provide > 99% power to detect the treatment effect, accounting for a conservative estimate of 13% attrition. If more participants gain competitive employed in the control arm (~50%), there will be >80% power to detect this effect.

Aim 2: Health and recovery outcomes. Two-level linear regression models accounting for the nested nature of the data (repeated measures nested within individuals) will be used to examine the effects of CBTw + SE services compared to psychoeducation + SE on the change of each of the continuous outcomes including recovery (RAS), health-related quality of life (PCS & MCS), symptoms (DSM), and suicidality (SSI) over time (baseline and 3-, 6-, 9-months follow-ups). It is expected that there will be adequate power (>80%) to detect the treatment effect on health and recovery outcomes even if the effect size is small (i.e., $f^2 = .03$). *Regarding the outcome of suicidal ideation, it is anticipated that the range of responses will be smaller, given that fewer participants will report these thoughts (21.2% of participants in the CBTw open pilot reported passive ideation at baseline; 9.6% reported such thoughts at follow up). Thus, the study may be less powered to detect a treatment effect. However, despite this issue of range restriction given the relatively lower base rate of suicidal thoughts, WORKWELL will nonetheless examine possible treatment effects, due to the importance of this outcome in Veterans with SMI.*

Preliminary analysis: Baseline characteristics of sample & covariates analyses

Given the RCT design, characteristics of participants are expected to be balanced across the two study arms. Baseline characteristics and baseline clinical outcomes (e.g., symptoms) will be compared between the arms using the appropriate test (i.e., t-test, or Chi-square test). Variables found to significantly differ will be included as covariates in the primary analyses. All primary analyses will also include time receiving SE services and site membership as covariates. The potential interaction effects of site with key predictors will also be included as predictors to account for the site effect. Lastly, attendance (the number of CBTw or psychoeducation sessions attended) and the association with the Aim 1 and Aim 2 outcomes will be examined.

Aim 1 Analyses: Competitive Work Outcomes

Hypothesis 1: For the outcome, total weeks worked in competitive jobs, three-level linear regression models will be used to test the effects of CBTw + SE compared to psychoeducation + SE over time, with predictors of study arm, arm by time interaction, site, and interaction between site and key predictors, covariates, as well as random effects to accommodate the potential non-independence due to repeated measures and group cohort effects. The time effects could be linear or nonlinear; these possibilities will be examined by treating time as continuous or categorical. If the outcomes are not normally distributed, robust maximum likelihood estimation method will be used to correct the standard error estimates for nonnormality. In the case of excess of zeros for this outcome, hurdle negative binomial models, a reliable method to analyze zero inflated longitudinal data of this nature, will be utilized. For the binary outcome, steady competitive work status across the 9-month study period, two-level logistic regression model will be used with the same set of predictors as in the linear models, with random effects to accommodate the potential non-independence due to group cohort effects.

Aim 2 Analyses: Health and Recovery Outcomes

To test **Hypothesis 2a**, Two-level linear regression models accounting for the nested nature of the data (repeated measures nested within individuals) will be used to examine the effects of CBTw + SE services compared to psychoeducation + SE on the change of each of the continuous outcomes including recovery (RAS), health-related quality of life (PCS & MCS), symptoms (DSM), and suicidality (SSI) over time (baseline and 3-, 6-, 9-months follow-ups). The scores of the outcome measures are calculated by averaging the corresponding items. The models are the same as those in Aim 1 analysis except that the outcomes are different. It is hypothesized that CBTw + SE will lead to a greater improvement on the health and recovery outcomes (indicated by a significant arm by time effect). If the outcomes are not normally distributed, robust maximum likelihood estimation method will be used to correct the standard error estimates for nonnormality.

To test **Hypothesis 2b**, two-level linear regression models will examine the effects of work on health and recovery outcomes over time, with predictors of competitive weeks worked, time, weeks by time interaction, site membership and potential interaction between site and key predictors, potential covariates (i.e. controlling for baseline levels of health and recovery), as well as random effects to accommodate the potential non-independence due to repeated measures and group cohort effects.

Missing data: Aims 1 & 2

Missing data from Aims 1 and 2 will come in two different forms: missing by attrition and intermittent missing of observation. Using logistic regression, the effects of missing observations due to sample attrition will be examined by investigating the participant characteristics associated with dropout. If results reveal that data are missing completely at random (MCAR) or due to observed factors (MAR), the data will be analyzed using full information maximum likelihood, taking into account potential predictors for missingness. However, if the pattern of missing data is nonignorable, pattern-mixture models that includes variables defined by the participant's pattern of missing data will be used. Sensitivity analyses also will be performed to examine how the result will change based on different assumptions about the missing data, such as the missing work period having no work, the mean amount of work as available data from earlier follow-up periods, or full employment.

Account for Heterogeneity in the Sample

The study is limited to working aged Veterans with SMI who are unemployed at baseline, decreasing the heterogeneity of the sample. In addition, analyses will examine whether treatment effect will change as a function of the site membership and major characteristics of the study participants, such as different types of SMI diagnoses, age, and current substance use (e.g., users vs. non-users).

AIM 3 CBTw IMPLEMENTATION: OVERVIEW

The initial CBTw implementation strategy was informed by implementation science and developed based on our experience in the two CBTw pilots, stakeholder surveys and interviews, and feedback from operational partners. *In order to ensure successful implementation of CBTw during WORKWELL and wide-scale uptake following its completion, an evaluation of this initial implementation strategy and barriers and facilitators of implementation will be conducted, guided by the RE-AIM framework.*

Initial Implementation Strategy

As identified in the ERIC guidelines and based on the procedures established in CBTw pilots and our experience implementing other psychosocial interventions.

- (a) **Implementation planning** (Months 1-2): During initial start-up, the study team will meet with SE staff and managers at sites to determine the best approach to integrating CBTw in work flow, and develop procedures to support implementation (e.g., documentation procedures). The study team will also work with sites to select intervention facilitators chosen from the VRCs at each SE program. **VRCs will deliver the CBTw and psychoeducation interventions (separate VRCs for each condition).** VRCs were chosen because they are present at most SE programs nationally (high generalizability potential) and have master's level training in both employment services and rehabilitation counseling. This implementation approach was suggested by [name] (VACO TSES Director) and endorsed by SE managers as appropriate and feasible.
- (b) **Training** (Months 1-3): [name], [name], [name] will conduct onsite training. VRCs delivering CBTw will attend a half-day CBTw workshop consisting of: 1) Education on CBTw content and application of cognitive, behavioral, and narrative strategies; 2) Mock practice of facilitation strategies; 3) Customization of CBTw content to meet unique needs of Veterans. Second, led by [name], psychoeducation facilitator training will follow a parallel structure. Third, other SE staff will be oriented to study procedures. Fourth, SE managers overseeing VRCs will receive training on how to provide supervision to ensure CBTw implementation.
- (c) **Fidelity monitoring & feedback** (~Monthly): Lead by [name], adherence to the CBT model will be assessed by the Cognitive Therapy Scale-Revised (CTS-R). All CBTw and psychoeducation sessions will be audio-recorded to rate fidelity. *At each site, 3 sessions from each group cohort (i.e. 1 session out of every 4) will be randomly selected for rating (in the CBTw and psychoeducation arms).* On a monthly basis, consultation lead by [name] and [name], will include review of fidelity scores and recommendations to improve as needed. *Psychoeducation facilitators will also be given fidelity feedback if they begin to drift toward CBT elements.*
- (d) **CBTw consultation** (weekly) will be led by [name] and [name] via tele or video with VRC CBTw facilitators and SE program managers. Consultation will feature the CBTw Facilitator Guide (Appendix 3) that was piloted in earlier work. In addition, strength based consultation will focus on Veteran case conceptualization, with an emphasis on understanding participants' recovery paths, applying CBTw strategies to fit goals and employment trajectories as they evolve over time, and problem solving obstacles.

Aim 3 RE-AIM Evaluation: Measures & Procedures guided by the RE-AIM Framework

- (a) **RE-AIM domains of implementation, adoption, and maintenance** will be examined through semi-structured **key stakeholders' interviews**. The interviews will also focus on understanding reasons to uptake and continue CBTw and important issues related to inner context and outer context (See Appendix 6). Interviews will also centrally focus on identifying notable
- (b) **RE-AIM implementation, the primary Aim 3 outcome**, will further be gauged using **fidelity assessment**. Fidelity will be measured by the CTS-R, comprised of 12 Likert items (scale of 0-6), with higher scores indicating greater adherence to the CBT model. Acceptable fidelity is a score of 4 or higher, indicating item "proficiency". Used extensively, including in the CBTw open pilot, the CTS-R has strong reliability.
- (c) **Barriers and facilitators to CBTw implementation** within SE programs will be examined through stakeholder interviews with (Appendix 6), and further through virtual site visits (See Section E2d below).

- (d) **Virtual site visits** at pre-implementation (1 month), early implementation (~Month 6), mid-implementation (first quarter-Year 2), and later implementation (first quarter-Year 3) will be conducted. During day-long visits, Drs. [name] and [name] will interview VRCs delivering CBTw, SE staff and managers, and make observations of CBTw processes. The implementation support team will keep detailed field notes recording activities conducted, **barriers and facilitators** encountered, and **strategies utilized to address these**. Site visitors will produce a written report that will provide a narrative summary of implementation strengths and weaknesses.
- (e) **RE-AIM Reach** will be examined using **quantitative data**: *CBTw and psychoeducation completion, session attendance, study recruitment, attrition rates; these data will be collected and compared across arms.*

Aim 3 Analyses & Integration of Mixed Methods Data

A deductive-inductive rapid qualitative analysis process will be used to facilitate the timely use of qualitative data to refine the implementation strategy, an approach appropriate for the description of implementation processes and environments. ***Templated summaries*** of each data collection episode will be created, organizing quotes or observations by pre-established codes (the deductive component) pertaining to RE-AIM domains. Emergent themes in the data (the inductive component) will be captured through use of a grounded theory approach, allowing for discovery of themes not included in *a priori* codes. Field notes will be written after **site visit observations** and **staff interviews** will bolster data not captured in immediate data summaries. An iterative process will occur, in which analysis will begin at the first observation and will inform direction of future data collection. The team will then create a **matrix summarizing data by code and collection episode**. *This will facilitate examination of variation across respondents, identify data gaps, and develop summaries of data mapping onto RE-AIM domains, as well as barriers and facilitators encountered.*

Integration of Quantitative and Qualitative Data: **1)** Descriptive fidelity data and **2)** RE-AIM reach data will be calculated for each site. These data will be integrated with **3)** stakeholder interview and **4)** site visit data described above. **Integrated site summaries** will evolve across the study period and will facilitate on-going refinement and finalization of a CBTw implementation strategy bundle.

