### METHODS:

WORKWELL is a pragmatic, Hybrid 1 design RCT. CBTw will be tested at 3 SE sites—Roudebush VA Medical Center, the Edward J. Hines VA Medical Center, and the VA St. Louis Health Care System. 276 unemployed Veterans with SMI will be randomly assigned to receive CBTw plus regular supported employment services or a control of psychoeducation plus regular

supported employment services. Outcomes including total weeks worked in competitive jobs (primary study outcome), achievement of steady work, symptoms, recovery, health related quality of life, suicidal ideation, and service utilization will be assessed at posttreatment (12 weeks), 6 months (primary endpoint), and 9 months (to examine sustained effects). Competitive work outcomes will also be assessed at 12 months. Aim 1 and Aim 2 work and recovery outcomes will be analyzed using multilevel modeling to compare the intervention and control groups over time. CBTw implementation planning, training, and consultation will be provided to SE staff persons delivering the intervention. CBTw implementation outcomes will be analyzed using a rapid mixed methods approach.

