### 3.2. Specific Aims & Hypotheses.

Aim 1. Test the effects of CBTw + SE compared to a time and format matched active control of psychoeducation + SE on competitive work outcomes across the 9 month study period. A total of 276 unemployed Veterans with SMI will be randomized to CBTw + SE or the control arm of psychoeducation + SE. Assessed at posttreatment (12 weeks), 6 months (primary endpoint), 9 months and 12 months (to examine sustained effects), the primary outcome will be total weeks worked in competitive jobs. A secondary work outcome, achievement of steady competitive work (i.e. working at least 50% of the follow-up), will be compared between study arms across the 12 month follow up.

Hypothesis 1: Compared to the control arm, participants in the CBTw + SE arm will work significantly more weeks and will be more likely to become steady workers.

Aim 2. Test the effects of CBTw + SE compared to the control arm of psychoeducation + SE on health and recovery at posttreatment (12 weeks), 6 month and 9 month follow up periods. The study will determine the effectiveness of CBTw to improve key health and recovery outcomes including health-related quality of life, suicidal ideation, subjective recovery, symptoms, and mental health service utilization.

Hypothesis 2a: Compared to controls, participants in the CBTw + SE arm will have greater improvement on subjective recovery and health-related quality of life, and decreases in mental health symptoms, suicidal ideation, and inpatient service utilization.

Hypothesis 2b: Greater participation in competitive work will predict improvements in these outcomes over time.

Aim 3. Guided by the RE-AIM implementation framework, conduct an implementation evaluation of CBTw to inform future wide scale roll-out of the intervention across the VHA. Existing Vocational Rehabilitation Counselors (VRCs) at the 3 VA SE programs will deliver CBTw, supported by an initial implementation strategy bundle—site tailored implementation planning, CBTw training, and weekly consultation including audit and feedback. Informed by the RE-AIM implementation framework, data will be collected and utilized to tailor implementation during the study, with assessment of the following RE-AIM domains:

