## 5.6 Study Evaluations

### Data Collection Protocol for Study Aims 1 & 2

Conducted by onsite research assistants (RAs) blinded to arm assignment, outcomes assessments will take place at four time points: baseline, 12-weeks (posttreatment), 6 months, and 9 months. In addition, work outcomes will be collected monthly on Work Update Forms to lessen the burden of Veteran recall. This schedule will elucidate the trajectory of treatment effects over time, including early response and more sustained impacts on outcomes. Participants will receive \$20 for each completed outcome assessment (baseline, 12-week, 6 & 9 month only). After obtaining informed consent, the onsite RA will administer a baseline assessment to gather assessment data. Each assessment will take approximately 60 minutes. All baseline assessments will take place in person; 12 week, 6 month, and 9 month assessments may be done in person (first consideration) or by phone.

The primary work outcome, total weeks worked in competitive jobs, will be collected monthly and analyzed at all assessment points with the primary endpoint being 6 months to allow adequate time for CBT skills to be practiced and solidified. The 12 month endpoint will examine whether there are sustained effects of CBTw and determine whether there are differences between the arms on achievement of steady competitive work (Aim 1). Health and recovery outcomes will be examined between the arms at all assessment points to understand the impact of CBTw; the relationship between weeks worked and these outcomes will also be examined at all assessment points (Aim 2). Work outcomes may be collected in person or by phone.

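### The SAP names 6 and 9 months as primary endpoints and the protocol only 6; with no decision rule or deciding contrast, primary success at either time is not ruled out

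*SAP*

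**What the plan says.** The protocol is consistent on the primary time point:

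- Abstract, Methods: "6 months (primary endpoint), and 9 months (to examine sustained effects".
- Section 3.2, Aim 1: "6 months (primary endpoint), 9 months and 12 months (to examine sustained effects".
- Section 5.6, Study Evaluations: weeks worked are "analyzed at all assessment points with the primary endpoint being 6 months". A clinical reason follows, that participants need time to practise the CBT skills.

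The SAP (Sample size and power, Aim 1) says instead that "the primary outcome is total weeks worked in competitive jobs with primary endpoints of 6 and 9 months".

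The only error rate in the SAP is in the same paragraph. It says "there will be 97.6% power to detect even a small study arm by time interaction effect", at f² = .03, "with type I error set at .05".

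The Hypothesis 1 analysis is a three-level longitudinal model "with predictors of study arm, arm by time interaction, site, and interaction between site and key predictors", plus covariates and random effects. Time may be continuous or categorical. No between-arm contrast at month 6 or month 9 is named, and month 12 does not appear in the SAP's analyses.

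**The concern.** The two documents disagree about which result makes the trial positive. Suppose the arms do not differ at month 6 but do at month 9. Under the protocol the primary endpoint is not met. Under the SAP one of two primary endpoints is met, and nothing says whether that is enough. With no order, split or both-required rule, the type I error of the primary claim is undefined, and under the most permissive reading it exceeds 5%.

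The model does not settle the matter. If time is continuous and linear, the arm-by-time term compares slopes over the whole follow-up and is not a month-6 or month-9 comparison. If time is categorical, a contrast is available at each visit, and the SAP does not say which one decides.

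**Working it through.** **1. Inputs.** Primary time points: 6 and 9 months (SAP), 6 months (protocol). Alpha .05, sidedness not stated, taken as two-sided. Power 97.6% for the arm-by-time interaction at f² = .03. ICCs of .077 (cohort) and .2 (repeated measures). Sample 276, with 13% attrition: 276 × 0.87 = 240. Groups of up to 8. The correlation between the 6- and 9-month results is not given and has to be assumed.

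**2. The SAP's own power figure.** The simulation's variances, time points and time coding are not reported, so only an approximation is possible: noncentral F, 1 numerator df, noncentrality = f² × effective observations. Design effects are 1 + 7 × .077 = 1.539 for cohort and, with three time points assumed, 1 + 2 × .2 = 1.4 for repeated measures.

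- 240 × 3 / 1.4 = 514.3; noncentrality .03 × 514.3 = 15.4; power 97.5%.
- 276 × 3 / 1.539 = 538.0; noncentrality 16.1; power 98.0%.
- Both design effects: 92.3% (276) or 88.4% (240).
- A closed-form slope contrast over three time points: 99.9% (276) or 99.6% (240).

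The 97.6% is plausible but cannot be confirmed. It describes the interaction and not a month-6 difference.

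**3. Error rate if each time is tested at .05 and either suffices.** For test statistics Z₆ and Z₉, bivariate normal with correlation r:

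family-wise error = 1 − P(|Z₆| < 1.96, |Z₉| < 1.96)

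| assumed r | either suffices | both required (.05 + .05 − either) |
|---|---|---|
| 0 | .0975 | .0025 |
| .70 | .0835 | .0165 |
| .80 | .0781 | .0219 |
| .90 | .0704 | .0296 |
| .95 | .0646 | .0354 |

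The last column is for no effect at either time. If there is an effect at one time only, the both-required error can rise to .05 but not above it.

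**4. Which correlations are plausible.** If weeks are totalled from the start, the two totals share 26 of 39 weeks. With independent weeks of equal variance, r = √(26/39) = .816 and the error is .077. Work is persistent, so r is probably higher. Null simulations with 120 per arm and five assumed patterns of job start and tenure (4,000 runs each) gave r of about .90 to .95 and an either-suffices error of .062 to .075. The simulation standard error is about √(.065 × .935 / 4000) = .004. If weeks were counted per interval (0–6 and 6–9 months), the same simulations gave .081 to .093.

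**5. Error rate if one test decides.** A single pre-named arm-by-time test at .05 has error .05, however many time points are called primary.

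**6. Cost of the remedies.** A single month-6 test, or a fixed order of 6 then 9 months, keeps each test at .05. A Bonferroni split uses .025 per test. By the normal approximation, a test with 97.6% power has 1.960 + 1.977 = 3.937; 3.937 − 2.241 = 1.696, so power falls to 95.5%. A test with 80% power has 1.960 + 0.842 = 2.802; 2.802 − 2.241 = 0.560, so power falls to 71.2%. Holding power would take about 317 or 335 participants respectively, instead of 276.

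**The case against.** The strongest reply is that the SAP describes one longitudinal model and one powered term. The .05 belongs to the power statement for the arm-by-time interaction and is not assigned to each time point. The SAP also says its Aim 2 models match those of Aim 1, and it judges Aim 2 by the arm-by-time effect. If the same test decides Aim 1, naming two time points inflates nothing. Two primary endpoints can also mean that both must succeed, which keeps the error at or below .05.

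Much of this stands. A reader might infer that the primary claim has two chances at .05, or that its error is near 10%. The documents do not support either statement. They specify no separate 6- and 9-month tests and no either-suffices rule, and 9.75% requires independent results, which totals sharing 26 of 39 weeks would not give. The size of any inflation also rests on assumed correlations.

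The reply does not remove the gap. The deciding term is stated for Aim 2 and left unstated for Hypothesis 1. With the time coding open, the interaction is either a slope or a set of visit contrasts. If one overall interaction were meant to decide, it is unclear what naming two primary endpoints adds. The disagreement with the protocol remains on any reading.

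**Conclusion.** The contradiction is certain: the SAP has two primary endpoints, the protocol has one, and neither document explains the difference or gives a rule. The SAP permits, without stating it, a claim of primary success at either time.

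The consequence for type I error is conditional. With two-sided tests at .05 and either sufficient, it is about 6.5% to 8.4% for assumed correlations of .95 to .70. Cumulative weeks under the simulated work patterns give about 6.2% to 7.5%. It is 5% or less if a single pre-named test decides or both times must succeed. The inflation is moderate, but it falls on the trial's main claim, and the meaning of a null month-6 result with a positive month-9 result depends on which document is followed. It should be corrected before the primary result is read.

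**What to change.** In the SAP's Aim 1 paragraph, make total competitive weeks through month 6 the sole primary endpoint, as in the protocol. Make month 9 secondary, followed by month 12 if it is analysed as the protocol states, each tested at .05 in fixed sequence only if the preceding test is significant.

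In the SAP's Hypothesis 1 analysis, name the between-arm contrast at month 6 that decides the hypothesis, and fix the time coding that yields it (categorical time, for example). Changing the endpoint sentence alone would leave the model without a defined month-6 test.

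A split alpha or a both-required rule would also control the error. The first costs power, as shown in the working, and the second demands success twice. Both depart from the protocol's single endpoint.

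The change costs a few sentences and needs no alpha split. Month 9 alone can no longer carry the primary claim. The 97.6% power was computed for the arm-by-time interaction and should be confirmed or restated for the named month-6 contrast.
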